#### 1.32 Clinical Experience

Current clinical studies of atezolizumab include one ongoing phase 1a monotherapy study, three ongoing combination studies, five phase 2 studies, and one phase 3 study. Details of all ongoing studies can be found in the Atezolizumab Investigator's Brochure.

#### 1.4 Rationale for combination of anetumab ravtansine and atezolizumab in mesothelin-expressing NSCLC

Although the results with immunotherapy are encouraging as compared to the standard chemotherapy, a proportion of patients that have been treated with immunotherapy eventually experience disease relapse. This phenomenon has sometimes been attributed to tumor escape mechanisms or T-cell exhaustion. The patients who do not respond to these agents are noted to have an inability to mount an immune attack due to poor antigenicity. The use of AR could theoretically overcome this barrier to response. Mechanistically, AR binds to human mesothelin and internalizes the antigen, DM4 binding then results in disruption of microtubule dynamics and cell death which could result in the release of neoantigens. This increased antigenic burden could synergize with the restored T-cell function due to PD-L1 blockade and result in increased cell death. Preliminary data in ovarian cancer mice models have confirmed a synergistic effect between ADCs and PD1 inhibitors. In addition, trastuzumab emtansine (T-DM1) renders HER2+ breast cancer highly susceptible to CTLA-4/PD-1 blockade (19).

#### 1.5 Rationale for Correlative Studies

The Mayo Clinic group led by [name] was the first to describe soluble PDL-1 (sPDL-1) as a potential predictive biomarker of efficacy of PD1/PDL1 inhibitors. His data indicate that high levels of circulating sPDL-1 are associated with poor clinical

outcomes in melanoma patients. His group went on to demonstrate in a cohort of 80 melanoma patients that none of those patients with detectable sPDL-1 in their blood responded to treatment with pembrolizumab. (Dronca R, Harrington SM, Enninga EAL, et al.). Thus, sPD-L1 may represent a blood-based biomarker of resistance to PD-1/PDL-1 inhibition. In addition, this group has demonstrated that Bim is overexpressed in a tumor-reactive T cell subset ( $T_{TR}$ ) that engages with PD-L1 expressing tumors. Not only was upregulation of Bim in circulating  $T_{TR}$  a negative prognostic factor in a historic group of patients with metastatic melanoma who did not receive immunotherapy, but upregulation of Bim in circulating  $T_{TR}$  was also predictive of responses to the PD-1 inhibitor pembrolizumab in a more recent cohort of patients. Moreover, Bim levels in circulating  $T_{TR}$  decreased in both responders and those with pseudo-progression. Based on these data, we will evaluate levels of sPD-L1 and upregulation of Bim in  $T_{TR}$  as blood-based biomarkers in this trial.

## 2.0 Goals

### 2.1 Primary Goals

#### Phase I

To identify the recommended phase II dose of anetumab ravtansine combined with atezolizumab in advanced MSLN+ NSCLC.

#### Phase II

To determine the confirmed response rate for the combination of anetumab ravtansine and atezolizumab in MSLN+ 2nd line NSCLC

### 2.2 Secondary Goals

#### Phase I

2.21 To describe adverse events and toxicities of the combination treatment of anetumab ravtansine and atezolizumab

2.22 To identify preliminary evidence of clinical activity (i.e. response, timed endpoints, etc.)

#### Phase II

2.23 To determine the progression-free survival (PFS) and the 1-year PFS rate for the combination of anetumab ravtansine and atezolizumab in 2nd-line NSCLC

2.24 To determine the overall survival of anetumab ravtansine combined with atezolizumab in second-line therapy of NSCLC

2.25 Adverse events will also be summarized as well.

### 2.3 Correlative Goals

2.31 To determine using flow cytometry the levels of Bcl-2 interacting mediator of cell death (BIM) in circulating CD8+ CD11a+ PD-1+ T-cells, in peripheral blood samples collected from patients prior to initiation of therapy (baseline) and correlating these with confirmed response rate during and following treatment with the combination regimen.

2.32 To determine tissue MSLN and PD-L1 expression and correlate with response to combination therapy with atezolizumab and anetumab ravtansine

2.33 To correlate baseline serum soluble PDL-1 (sPDL-1) with response to therapy.

### 3.0 Patient Eligibility

**Phase I only: Prior to discussing protocol entry with the patient, call the MCCC Registration Office at [REDACTED] for dose level and to ensure that a place on the protocol is open to the patient.**

#### 3.1 Pre Registration - Inclusion Criteria

- 3.11 Ability to understand and the willingness to sign a written informed consent document.
- 3.12 Age  $\geq 18$  years.
- 3.13 Patient has disease amenable to biopsy if the archival tissue sample is unavailable. Note: Archive sample must not be older than 36 months.

#### 3.2 Registration - Inclusion Criteria

- 3.21 **Phase I only:** Diagnosis of advanced/metastatic NSCLC for which no standard treatment option. **Phase II only:** Advanced NSCLC patients who have received at least 1 platinum-based systemic chemotherapy regimen
- 3.22 Patients with tumors having actionable genomic alterations should have received prior therapy with FDA approved agents targeting these alterations (ie EGFR, ALK, ROS1, BRAF V600E)
- 3.23 ECOG performance status 0 or 1. (See Appendix A)
- 3.24 **Phase II only:** Must have at least one measurable lesion as defined by RECIST criteria (see Section 11).
- 3.25 Ability to understand and the willingness to sign a written informed consent document.
- 3.26 Histological or cytologically confirmed NSCLC that shows moderate or stronger mesothelin expression in 30% of tumor cells by a companion assay. MSLN expression score using Ventana IHC SP74 assay. Phase I only: In addition 5-30% tumor cells and 1, 2, or 3+ MSLN score. Phase II only: 30% tumor cells and either 2+/3+.
- 3.27 Life expectancy of  $\geq 12$  weeks.
- 3.27 Adequate bone marrow and organ function as defined by the following laboratory values  $\leq 14$  days prior to registration:
  - Absolute neutrophil count  $\geq 1.5 \times 10^9/L$
  - Platelets  $\geq 100 \times 10^9/L$
  - Hemoglobin  $\geq 9$  g/dL
  - Chemistries as follows:
    - Potassium  $\geq$  lower limit of normal (LLN) range for the institution
    - Calcium  $\geq$  LLN (corrected for serum albumin, if albumin abnormal)
    - Magnesium  $\geq$  LLN
    - Sodium  $\geq$  LLN
    - Phosphorus  $\geq$  LLN.
 NOTE: Supplementation may be given before the first dose of study medication.
  - INR  $\leq 1.5$

- Serum creatinine  $\leq 1.5$  mg/dL or creatinine clearance  $\geq 50$  mL/min (calculated by Cockcroft Gault equation)

**Cockcroft-Gault Equation:**

$$\text{Creatinine clearance for males} = \frac{(140 - \text{age})(\text{weight in kg})}{(72)(\text{serum creatinine in mg/dL})}$$

$$\text{Creatinine clearance for females} = \frac{(140 - \text{age})(\text{weight in kg})(0.85)}{(72)(\text{serum creatinine in mg/dL})}$$

- ALT and AST  $\leq 2.5$  x ULN or  $\leq 5$  x ULN if liver metastases are present.
  - Total bilirubin  $\leq 1.5$  x ULN
- 3.28 Standard 12-lead ECG with the following parameters at screening (defined as the mean of the triplicate ECGs):
- QTcF interval at screening  $< 450$  msec (using Fridericia's correction)
- 3.29a Negative pregnancy test performed  $\leq 7$  days prior to registration (women of childbearing potential only).
- 3.29b Willing to return to enrolling institution for follow-up (during the Active Monitoring Phase of the study)
- 3.29c Willing to provide blood samples for correlative research purposes
- 3.3 Registration - Exclusion Criteria
- 3.31 Prior treatment with anti-PD-1, or anti-PD-L1 antibody which resulted in a patient having serious (grade 3-4) immune related adverse events.
- Note:
- Patients who have received prior treatment with anti-CTLA-4 may be enrolled, provided the following requirements are met:
    - Minimum of 12 weeks from the first dose of anti-CTLA-4 and  $>6$  weeks from the last dose
    - No history of severe immune-related adverse effects from anti-CTLA-4 (NCI CTCAE Grade 3 and 4)
- 3.32 More than one prior taxane regimen at any stage of the disease under study ("taxane" refers to paclitaxel, docetaxel, Abraxane® and cabazitaxel). Adjuvant and/or neoadjuvant treatments are considered together as one prior regimen.
- 3.33 Treatment with any other investigational agent or investigational device within 4 weeks prior to registration (or within five half-lives of the investigational product, whichever is longer). Patients must be  $\geq 2$  weeks since any investigational agent administered as part of a Phase 0 study (also referred to as an "early Phase I study" or "pre-Phase I study" where a sub-therapeutic dose of drug is administered) at the Coordinating Center PI's discretion, and should have recovered to eligibility levels from any toxicities.
- 3.34 Treatment with systemic immunostimulatory agents (including, but not limited to, interferon- $\alpha$  or interleukin-2) within 6 weeks or five half-lives of the drug (whichever is shorter) prior to registration.

- 3.35 Received radiotherapy  $\leq 4$  weeks or limited field radiation for palliation  $\leq 2$  weeks prior to registration, and who has not recovered to Grade 1 or better from related side effects of such therapy (exceptions include alopecia) and/or in whom  $\geq 25\%$  of the bone marrow was irradiated.
- 3.36 Patients who have a previous or concurrent cancer that is distinct in primary site or histology from the cancer being evaluated in this study, except
- Cervical carcinoma in situ, non-melanoma skin cancer, superficial non-invasive bladder tumors, DCIS or any previous cancer curatively treated  $> 3$  years before the start of anetumab ravtansine.
- 3.37 Treatment with systemic immunosuppressive medications (including, but not limited to, prednisone, cyclophosphamide, azathioprine, methotrexate, thalidomide, and anti-tumor necrosis factor [anti-TNF] agents)  $\leq 2$  weeks prior to registration.
- Note:
- Patients who have received acute, low dose, systemic immunosuppressant medications (e.g., a one-time dose of dexamethasone for nausea) may be enrolled.
  - The use of inhaled corticosteroids and mineralocorticoids (e.g., fludrocortisone) for patients with orthostatic hypotension or adrenocortical insufficiency is allowed.
- 3.38 Patients with known primary central nervous system (CNS) malignancy or symptomatic CNS metastases are excluded, with the following exceptions:
- Patients with asymptomatic untreated CNS disease may be enrolled, provided all of the following criteria are met:
    - Evaluable or measurable disease outside the CNS
    - No metastases to brain stem, midbrain, pons, medulla, cerebellum, or within 10 mm of the optic apparatus (optic nerves and chiasm)
    - No history of intracranial hemorrhage or spinal cord hemorrhage
    - No ongoing requirement for dexamethasone for CNS disease; patients on a stable dose of anticonvulsants are permitted.
    - No neurosurgical resection or brain biopsy  $\leq 28$  days prior to registration
  - Patients with asymptomatic treated CNS metastases may be enrolled, provided all the criteria listed above are met as well as the following:
    - Radiographic demonstration of improvement upon the completion of CNS-directed therapy and no evidence of interim progression between the completion of CNS-directed therapy and the screening radiographic study
    - No stereotactic radiation or whole-brain radiation  $\leq 28$  days prior to registration
    - Screening CNS radiographic study  $\geq 4$  weeks from completion of radiotherapy and  $\geq 2$  weeks from discontinuation of corticosteroids
- 3.39a History of severe allergic, anaphylactic, or other hypersensitivity reactions to chimeric or humanized antibodies or fusion proteins
- 3.39b Patients who have a history or current evidence of bleeding disorder, i.e., any hemorrhage/bleeding event of CTCAE Grade  $\geq 2$ ,  $\leq 28$  days prior to registration.

- 3.39c History or current evidence of uncontrolled cardiovascular disease including, but not limited to, the following conditions:
- Congestive heart failure of New York Heart Association (NYHA, refer to appendix C) Class III or IV.
  - Unstable angina (symptoms of angina at rest) or new-onset angina  $\leq 6$  months before the start of anetumab ravtansine.
- 3.39d Uncontrolled intercurrent illness including, but not limited to, ongoing or active infection, symptomatic congestive heart failure, unstable angina pectoris, cardiac arrhythmia, or psychiatric illness/social situations that would limit compliance with study requirements.
- 3.39e Pregnant women are excluded from this study because atezolizumab is an investigational agent with the unknown potential for teratogenic or abortifacient effects. Note: Because there is an unknown but potential risk for adverse events in nursing infants secondary to treatment of the mother with atezolizumab, breastfeeding should be discontinued if the mother is treated with atezolizumab.
- 3.39f Patients on supraphysiologic doses of steroids or use of such  $\leq 6$  weeks prior to registration.
- 3.39g Known clinically significant liver disease, including active viral, alcoholic, or other hepatitis; cirrhosis; fatty liver; and inherited liver disease.

Note:

- Patients with past or resolved hepatitis B infection (defined as having a negative hepatitis B surface antigen [HBsAg] test and a positive anti-HBc [antibody to hepatitis B core antigen] antibody test) are eligible.
  - Patients positive for hepatitis C virus (HCV) antibody are eligible only if polymerase chain reaction (PCR) is negative for HCV RNA
- 3.39h History or risk of autoimmune disease, including, but not limited to, systemic lupus erythematosus, rheumatoid arthritis, inflammatory bowel disease, vascular thrombosis associated with antiphospholipid syndrome, Wegener's granulomatosis, Sjögren's syndrome, Bell's palsy, Guillain-Barré syndrome, multiple sclerosis, autoimmune thyroid disease, vasculitis, or glomerulonephritis.

Note:

- Patients with a history of autoimmune hypothyroidism on a stable dose of thyroid replacement hormone are eligible.
- Patients with controlled Type 1 diabetes mellitus on a stable insulin regimen are eligible.
- Patients with eczema, psoriasis, lichen simplex chronicus or vitiligo with dermatologic manifestations only (e.g., patients with psoriatic arthritis would be excluded) are permitted provided that they meet the following conditions:
  - Patients with psoriasis must have a baseline ophthalmologic exam to rule out ocular manifestations
  - Rash must cover less than 10% of body surface area (BSA)
  - Disease is well controlled at baseline and only requiring low potency topical steroids (e.g., hydrocortisone 2.5%, hydrocortisone butyrate)

- 0.1%, flucinolone 0.01%, desonide 0.05%, acemetasone dipropionate 0.05%)
- No acute exacerbations of underlying condition within the last 12 months (not requiring psoralen plus ultraviolet A radiation [PUVA], methotrexate, retinoids, biologic agents, oral calcineurin inhibitors; high potency or oral steroids)
- 3.39i History of idiopathic pulmonary fibrosis, pneumonitis (including drug induced), organizing pneumonia (i.e., bronchiolitis obliterans, cryptogenic organizing pneumonia, etc.), or evidence of active pneumonitis on screening chest computed tomography (CT) scan. Note: History of radiation pneumonitis in the radiation field (fibrosis) is permitted.
- 3.39j Severe infections  $\leq 4$  weeks prior to registration, including, but not limited to, hospitalization for complications of infection, bacteremia, or severe pneumonia.
- 3.39k Signs or symptoms of infection  $\leq 2$  weeks prior to registration.
- 3.39l Major surgical procedure  $\leq 28$  days prior to registration or anticipation of need for a major surgical procedure during the course of the study.
- 3.39m Patients with corneal epitheliopathy or any eye disorder that may predispose the patients to this condition as judged by an ophthalmologist.
- Note: Low grades of superficial punctate keratitis, within the range seen in the normal population, should not lead to the exclusion of the patient.
- 3.39n Non-healing serious wound, ulcer, or bone fracture unrelated to the primary tumor.
- 3.39o Previous assignment to treatment during this study. Patients permanently withdrawn from study participation will not be allowed to re-enter the study.
- 3.39p Substance abuse, psychological, or social conditions that may interfere with the patient's participation in the study or evaluation of the study results.

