### 1.2 Anetumab ravtansine (BAY 94-9343)

Anetumab ravtansine (BAY 94-9343) is an antibody-drug conjugate (ADC) targeting mesothelin, a protein normally present on mesothelial cells and overexpressed in the majority of mesotheliomas. Mesothelin expression is seen in approximately 40-60% patients with NSCLC (4, 5) The expression profile as well as the fact that mesothelin is an internalizing antigen highlights mesothelin as an adequate target for antibody-mediated delivery of cytotoxics. The biological function of mesothelin is unknown; mesothelin-deficient mice do not display a specific phenotype (6).

Anetumab ravtansine is a fully human IgG1 antibody (MF-T, BAY 86-1903) directed at the mesothelin antigen and conjugated to a synthetic maytansine derivative as toxophore (DM4, BAY 100-6640) by a disulfide linker moiety to its lysine residues. DM4 is a

spindle poison, and its mechanism of action (MoA) is inhibition of microtubule assembly (similar to that of vinca alkaloids).

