### 1.3 Atezolizumab

Atezolizumab is a human monoclonal antibody directed against programmed death-ligand 1 (PD-L1) with potential immune checkpoint inhibitory and antineoplastic activities.

Atezolizumab targets immune cells or tumor cells and prevents interaction with either programmed death-1 (PD-1) receptor or B7.1 (CD80), both of which function as inhibitory receptors expressed on T cells. Interference of the PD-L1: PD-1 and PDL1: B7.1 interactions may enhance the magnitude and quality of the tumor-specific T-cell response through increased T-cell priming, expansion, and/or effector function (8, 9) . In May 2016, atezolizumab (Tecentriq™) was approved for the treatment of patients with locally advanced or metastatic urothelial carcinoma whose disease had worsened during or following platinum-containing chemotherapy, or within 12 months of receiving platinum-containing chemotherapy.

Atezolizumab was engineered to eliminate Fc-effector function via a single amino acid substitution at position 298 on the heavy chain, which results in a non-glycosylated antibody that has minimal binding to Fc receptors and, consequently, eliminates detectable Fc-effector function. By eliminating Fc-effector function and antibody dependent cell-mediated cytotoxicity (ADCC), antibody-mediated clearance of activated effector T cells is also eliminated.

PD-L1 expression is prevalent in many human tumors (e.g., lung, bladder, ovarian, melanoma, colon carcinoma), and its overexpression has been associated with poor prognosis in patients with several cancers (9-12). PD-L1 binds to two known receptors, PD-1 and B7.1 (CD80). PD-1 is expressed on activated T cells, and receptor expression is sustained in states of chronic stimulation such as chronic infection or cancer (13, 14) .

Ligation of PD-L1 with PD-1 inhibits T-cell proliferation, cytokine production, and cytolytic activity, leading to the functional inactivation or inhibition of T cells. Similarly, while the receptor B7.1 has been best defined as a costimulatory molecule expressed by B lymphocytes and other antigen-presenting cells (APCs), B7.1 expressed on the surface of T cells may provide an additional signaling mechanism through which PD-L1 can negatively regulate T cell responses (8). As a result, aberrant expression of PD-L1 on tumor cells and tumor-infiltrating immune cells, such as macrophages and dendritic cells, has been reported to impede anti-tumor immunity and contribute to immune evasion (15, 16)

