## **8.2 Treatment Delay and Dose Reduction of Atezolizumab**

### **8.21 General AE Management and Dose Modification Guidelines**

There will be no dose reduction for atezolizumab in this study. Patients may temporarily suspend study treatment for up to 84 days (12 weeks) beyond the scheduled date of delayed infusion if study drug-related toxicity requiring dose suspension is experienced. If atezolizumab is held because of AEs for  $\geq 84$  days beyond the scheduled date of infusion, the patient will be discontinued from atezolizumab and will be followed for safety and efficacy as specified in this protocol.

If a patient must be tapered off steroids used to treat AEs, atezolizumab may be held for additional time beyond 84 days (12 weeks) from the scheduled dose until steroids are discontinued or reduced to a prednisone dose (or dose equivalent) of 10 mg/day. The acceptable length of interruption will be at the discretion of the investigator.

Dose interruptions for reasons other than toxicity, such as surgical procedures, may be allowed.

Any toxicity associated or possibly associated with atezolizumab treatment should be managed according to standard medical practice. Additional tests, such as autoimmune serology or biopsies, may be used to determine a possible immunogenic etiology. Although most immune-related adverse events (irAEs) observed with immunomodulatory agents have been mild and self-limiting, such events should be recognized early and treated promptly to avoid potential major complications (20) (Appendix C). Discontinuation of atezolizumab may not have an immediate therapeutic effect, and there is no available antidote for atezolizumab. In severe cases, immune-related toxicities may be acutely managed with topical corticosteroids, systemic corticosteroids, or other immunosuppressive agents. The investigator should consider the benefit-risk balance prior to further administration of atezolizumab. In patients who have met

the criteria for permanent discontinuation, resumption of atezolizumab may be considered if the patient is deriving clinical benefit and has fully recovered from the immune-related event.

Patients can be re-challenged with atezolizumab ONLY after careful consideration of benefit- risk balance and medical judgment by the trial Principal Investigator. Atezolizumab may NOT be resumed if the patient experiences any of the following events, regardless of benefit:

- Grade 3 or 4 pneumonitis

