- AST or ALT  $>5\times$ ULN or total bilirubin  $>3\times$ ULN
- Grade 4 diarrhea or colitis
- Grade 4 hypophysitis
- Any grade myasthenic syndrome/myasthenia gravis, Guillain-Barré, or meningoencephalitis
- Grade 3 or 4 ocular inflammatory toxicity
- Grade 4 or any grade of recurrent pancreatitis
- Grade 3 or 4 infusion-related reactions
- Grade 4 rash

Treatment may, under limited and compelling circumstances, be resumed in patients who have recovered from the following events after consultation with the trial Principal Investigator:

- Grade 2 pneumonitis
- Grade 2 ocular inflammatory toxicity
- Grade 2 infusion-related reactions

For detailed information regarding management of adverse events associated with atezolizumab, please refer to the most current version of the Atezolizumab Package Insert and the FDA product label.

The primary approach to grade 1 to 2 irAEs is supportive and symptomatic care with continued treatment with atezolizumab; for higher-grade irAEs, atezolizumab should be withheld and oral and/or parenteral steroids administered. Recurrent grade 2 irAEs may also mandate withholding atezolizumab or the use of steroids. Assessment of the benefit-risk balance should be made by the investigator, with consideration of the totality of information as it pertains to the nature of the toxicity and the degree of clinical benefit a given patient may be experiencing prior to further administration of atezolizumab. Atezolizumab should be permanently discontinued in patients with life-threatening irAEs.

Patients should be assessed clinically (including review of laboratory values) for toxicity prior to, during, and after each infusion. If unmanageable toxicity due to atezolizumab occurs at any time during the study, treatment with atezolizumab should be discontinued.

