## 15.0 Drug Information

### 15.1 Anetumab Ravtansine (BAY 94-9343)

15.11 **Background:** Anetumab ravnansine is an antibody drug conjugate consisting of the monoclonal antibody BAY 86-1903 directed against the mesothelin antigen, a SPDB- (N-succinimidyl-4-(2-pyridyldithio) butanoate) linker and the tubulin polymerization inhibitor N-methyl-N- [4-mercapto-4-methyl-1-oxopentyl-L-alanine ester of maytansinol (DM4; BAY 1006640).

15.12 **Formulation:** Anetumab ravnansine is supplied as a freeze-dried product containing 60 mg anetumab ravnansine in a 30 mL injection vial. The following excipients are used to manufacture the medicinal drug product: histidine, hydrochloric acid, glycine, sucrose, polysorbate 80, and water for injection.

15.13 **Preparation and storage:** Vials containing the freeze dried product should be stored at 2-8°C. The lyophilisate is reconstituted with 11.9 mL sterile water for injection to produce a 5 mg/mL solution of active substance. The solution is further diluted in 0.9% sodium chloride or dextrose 5% solution (in a PVC or non-PVC infusion bag) to a concentration range of 0.1-3 mg/mL. A slight turbidity may occur during the dilution which does not affect the quality of the drug product. The reconstituted and diluted solutions are physically and chemically stable for 24 hours at room temperature and between 2-8°C. However, unless administered immediately, for microbiologic consideration, the reconstituted and diluted solutions should be stored between 2°C and 8°C and used within 6 hours. Exposure to bright light should be avoided.

15.14 **Administration:** Infuse over 60 minutes using an in-line 0.2 micron infusion filter.

15.15 **Pharmacokinetic information:** (Based on limited information from a small sample size). Maximum plasma concentrations of the anetumab ravnansine and total antibody were typically observed within 1 hour of end of infusion and, at the MTD of 6.5 mg/kg every three weeks, concentrations declined with geometric mean terminal phase t1/2 values of approximately 5 to 6 days.

15.16 **Potential Drug Interactions:** No data available.

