#### 15.2 **Atezolizumab** for IV Administration

- 15.21 **Background:** Atezolizumab is a human immunoglobulin (IgG1) monoclonal antibody that is produced in Chinese hamster ovary (CHO) cells. Atezolizumab targets programmed death-ligand 1 (PD-L1) on immune cells or tumor cells and prevents interaction with either programmed death-1 (PD-1) receptor or B7.1 (CD80), both of which function as inhibitory receptors expressed on T cells. Interference of the PD-L1:PD-1 and PD-L1:B7.1 interactions may enhance the magnitude and quality of the tumor-specific T-cell response through increased T-cell priming, expansion, and/or effector function. Atezolizumab shows anti-tumor activity in various nonclinical models and is being investigated as a potential therapy for cancer patients with locally advanced or metastatic malignancies.
- 15.22 **Formulation:** Atezolizumab is supplied in a single use vial as a colorless-to-slightly-yellow, sterile, preservative-free clear liquid solution intended for IV administration. The vial is designed to deliver 20 mL (1200 mg) of atezolizumab solution but may contain more than the stated volume to enable delivery of the entire 20 mL volume. The atezolizumab drug product is formulated as 60 mg/mL atezolizumab in 20 mM histidine acetate, 120 mM sucrose, 0.04% polysorbate 20, pH 5.8.
- 15.23 **Preparation and storage:** Atezolizumab must be refrigerated at 2°C–8°C (36°F–46°F) upon receipt until use. No preservative is used in atezolizumab drug product; therefore, the vial is intended for single use only. Discard any unused portion of drug left in a vial. Vial contents should not be frozen or shaken and should be protected from direct sunlight. Atezolizumab is administered using 0.9% sodium chloride 250 mL IV bags and infusion lines equipped with

0.2 micron in-line filters (filter membrane of polyethersulfone [PES]). Bags may be constructed of polyvinyl chloride (PVC) or polyolefin (PO).

- 15.24 **Administration:** The initial dose of atezolizumab will be delivered over 60 ( $\pm$  15) minutes. If the first infusion is tolerated without infusion-associated adverse effects, the second infusion may be delivered over 30 ( $\pm$  10) minutes. If the 30-minute infusion is well tolerated, all subsequent infusions may be delivered over 30 ( $\pm$  10) minutes.
- 15.25 **Pharmacokinetic information:**  
**Distribution:**  $V_{dss}$ : 6.9 L  
**Half-life elimination:** 27 days  

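### Exclusion 3.39a omits human antibodies, the class of both study drugs, so Section 3 does not clearly exclude an earlier Grade 3-4 infusion or hypersensitivity reaction to a human anti-PD-L1 antibody

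*Combined protocol and SAP*

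**What the plan says.** Exclusion 3.39a bars patients with a "History of severe allergic, anaphylactic, or other hypersensitivity reactions to chimeric or humanized antibodies or fusion proteins". No other criterion in Section 3 deals with allergy, anaphylaxis or hypersensitivity.

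The protocol classes both study drugs differently from the antibodies in that list. Section 1.2: "Anetumab ravtansine is a fully human IgG1 antibody". Section 15.21: "Atezolizumab is a human immunoglobulin (IgG1) monoclonal antibody that is produced in Chinese hamster ovary (CHO) cells". Section 1.3 likewise calls atezolizumab human.

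Exclusion 3.31 does not rule out earlier anti-PD-1 or anti-PD-L1 treatment as such. It rules out treatment "which resulted in a patient having serious (grade 3-4) immune related adverse events".

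Once a patient is on study, Section 8.21 states: "Atezolizumab may NOT be resumed if the patient experiences any of the following events, regardless of benefit". One entry on the list that follows is "Grade 3 or 4 infusion-related reactions".

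**The concern.** A safety exclusion written for antibody reactions, applied as worded, misses the antibody class of both drugs being given. The patient of interest reacted severely to a human anti-PD-L1 antibody before the trial. If that reaction happens on study, the plan ends atezolizumab for good. If it happened before registration, Section 3 has no line that plainly stops the patient from being given the drug.

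What is at stake is the safety of an individual patient, and consistency between sites in how such a history is handled. The response endpoint, the Simon two-stage rule and the stated sample sizes do not depend on it.

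**Working it through.** This is a comparison of texts. The plan states no figure on this point to reproduce.

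**1. Does 3.39a reach the study drugs?** Its list has three classes: chimeric antibodies, humanized antibodies and fusion proteins. Sections 1.2, 1.3 and 15.21 call the two drugs human or fully human. In the plan's own terms, neither is on the list, and 3.39a does not name either drug.

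**2. Does 3.31 fill the gap?** It turns on whether a Grade 3-4 infusion reaction is an immune-related event. The plan does not say. The Section 8.22 table of potentially immune-related events has no row for infusion reactions, and Section 15.27 lists them under a miscellaneous heading. On the other side, the 8.21 list places them among events such as pneumonitis and colitis, directly after a discussion of immune-related events. The text leaves the question open.

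**3. Can a patient with such prior therapy reach registration?**
- 3.31 presupposes earlier anti-PD-1 or anti-PD-L1 treatment in some enrolled patients.
- 3.33 sets a washout for investigational agents, which implies that earlier use is acceptable.
- 9.49c, in Section 9.4 and so outside the Section 3 list, prohibits earlier systemic therapy that lacked approval for this indication. The only atezolizumab approval the documents record is for urothelial carcinoma (Section 1.3), and 3.39e calls the drug investigational.
- 9.49b prohibits earlier anetumab ravtansine, so a reaction to that drug itself cannot be the problem.

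For an anti-PD-L1 antibody as a class, 3.31 and 3.33 leave the route open. For atezolizumab in particular, the text is unsettled.

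**4. Does the plan carry other 8.21 events into entry?** Yes, for some. Earlier drug-induced pneumonitis is excluded by 3.39i, and Guillain-Barré syndrome by 3.39h. Infusion reaction has no equally clear counterpart.

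**5. How many patients?** For atezolizumab the count would be 49 × f × r × g, where:
- 49 is the maximum accrual (16.12);
- f is the share previously given atezolizumab, which the documents do not give;
- r is 1% to 10%, the 15.27 band for infusion-related reaction with no grade stated;
- g is the Grade 3-4 share of those reactions, which the documents do not give.

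Leaving out g and assuming f gives any-grade illustrations only:
- f = 0.10: 49 × 0.10 × 0.01 = 0.05 to 49 × 0.10 × 0.10 = 0.49
- f = 0.50: 49 × 0.50 × 0.01 = 0.25 to 49 × 0.50 × 0.10 = 2.45

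Both ranges overstate the Grade 3-4 count by an unknown factor and rest on an assumed f. They also leave out other human anti-PD-L1 antibodies, for which the documents give no rate. No Grade 3-4 number follows from them.

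**The case against.** The strongest objection is that the patient may not be admissible anyway. Read with the recorded urothelial approval and 3.39e, 9.49c can be taken to prohibit earlier atezolizumab for NSCLC. The urothelial route is largely closed by 3.36, which excludes most other cancers. Commercial supply (15.28) shows that the drug is marketed, not that it is approved for this disease. This stands in part: a reader might infer from 3.31 that earlier atezolizumab is plainly allowed, and the documents do not support that. Nor do they establish a bar, because 9.49c lies outside the eligibility section, fits poorly with 3.33, and does not mention hypersensitivity.

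Second, a site could reasonably treat a severe infusion reaction as falling under 3.31, or read 3.39a loosely. That is fair, but the outcome then depends on the reader.

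Third, 8.21 governs resumption, not entry, and its list is not applied uniformly: the 8.22 table lets patients resume after Grade 3 pneumonitis or Grade 3 uveitis following consultation with the principal investigator. The first part is correct, and 8.21 is used here only to show how the plan rates the event. On the second, the table contains no such relaxation for infusion reactions.

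Fourth, existing safeguards reduce the harm. Treatment starts under a medical oncologist (6.235), the first atezolizumab infusion runs about an hour (15.24), and patients are assessed before, during and after each infusion (8.21). These limit the consequences of re-exposure but do not prevent it.

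Finally, a reader might fault 3.39a for omitting excipients, since 15.12 lists "histidine, hydrochloric acid, glycine, sucrose, polysorbate 80, and water for injection" for anetumab ravtansine. No consequence of that omission can be shown from the documents, so it is not part of this point.

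**Conclusion.** The point holds as a wording gap. Section 3 does not clearly exclude a patient with an earlier Grade 3-4 infusion or hypersensitivity reaction to a human anti-PD-L1 antibody, including atezolizumab. The plan treats a Grade 3-4 infusion reaction on study as ending atezolizumab.

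A reader might go further and infer that the protocol knowingly admits such patients, or that a definite number will be exposed. Neither is supported: 3.31 and 9.49c can each be read to keep the patient out, and the number affected cannot be derived because prior exposure and the Grade 3-4 share are not given. It is likely very small.

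The conclusion rests on taking human as distinct from chimeric and humanized, as the plan's own drug descriptions do, and on 3.31 being silent about infusion reactions. There is no effect on the design or endpoints. Severity is minor. Confidence is moderate, because the status of prior atezolizumab is unsettled.

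**What to change.** Reword 3.39a along these lines: *Prior severe allergy, anaphylaxis or other hypersensitivity, or a Grade 3-4 infusion-related reaction, to a chimeric, humanized or human antibody, a fusion protein, or either study drug.* Naming the drugs' components is optional. With this wording, 3.31 needs no change.

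The cost is one amended criterion and the matching line on the eligibility checklist. No test is added. The downside is that a very few pretreated patients become ineligible.
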